## **E. The statistical analysis**

SPSS for Window 24.0 software will be used in statistical analysis. The type one error is 0.05. In inferences analysis, chi-square test, Pearson correlation coefficient, independent t test, one-way ANOVA and post hoc comparison (scheffe) test will be used to examine the variance among groups. Finally, ANCOVA and GEE mode will be used to test the effectiveness of intervention respectively.

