### **a. Stage 1:**

At this stage is a cross-sectional method and will be employed to investigate the relationship between smoking status and various physiological and psychological indicators in patients with CAD.

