### **b. Stage 2:**

At stage 2, subjects who are at the smoking cessation stage of "precontemplation" and "contemplation" will be recruited in this stage. A quasi-experimental design will be used to determine the effects of a four-week cognitive-behavioral education course related to smoking cessation on the participants' smoking cessation behavior, smoking decision-making, and self-efficacy in smoking cessation.

c. Stage 3:

Subjects who are at the "preparation" and "action" stage will be recruited and randomly divided into experimental or control group to identify the effect of a 12-week brisk walking on improving the participants' immediate (short-term), three-month, and six month (long-term) health status. The primary indicator used for health status evaluation is smoking cessation success rate; the secondary indicators used are physiological status (i.e., nicotine addiction, lung carbon monoxide concentration, heart rate variability, and smoking withdrawal syndrome) and psychological status (i.e., depression and

resilience).

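### Scheffé after one-way ANOVA is valid, but costs some precision if three or more groups are compared only in pairs; Tukey-Kramer would be narrower at the same 0.05

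*Combined protocol and SAP*

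**What the plan says.** Section E sets the error rate in one sentence, "The type one error is 0.05", without saying whether it applies per comparison or familywise. Among several methods for comparing groups it names "one-way ANOVA and post hoc comparison (scheffe) test". It does not say which variables or stage the ANOVA serves, how many groups it has, or which contrasts follow it. The independent t test is listed separately, so the natural reading is that ANOVA with a post hoc test is for three or more groups.

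Intervention effects are assigned elsewhere in the same section: "ANCOVA and GEE mode will be used to test the effectiveness of intervention respectively". In section D, Stage 3 patients are "randomly divided into experimental or control group", and "The primary indicator used for health status evaluation is smoking cessation success rate". Stage 1 is cross-sectional and is meant to "investigate the relationship between smoking status and various physiological and psychological indicators in patients with CAD". That makes Stage 1 the likeliest home for the ANOVA, although the document does not say so.

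**The concern.** Scheffé's margin is large enough to cover every linear contrast among the means, including pooled sets of groups. A post hoc step that only asks which groups differ from which needs protection for the pairwise differences alone. For that smaller family, Tukey-Kramer holds the familywise error at 0.05 with a smaller critical value whenever there are three or more groups. If the plan intends pairs only, it pays for protection that it does not use: intervals are wider, and true differences between groups are missed somewhat more often than an error rate of 0.05 requires.

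**Working it through.** **No figure to reproduce.** The document gives no sample size, power, effect size, standard deviation or number of ANOVA groups.

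**Inputs**
- From section E: Scheffé after one-way ANOVA, and α = 0.05.
- Assumed: k = 2 to 5 equal groups; n = 50 per group, with 20 and 100 as the range; pairwise comparisons only; 80% power per pair under Tukey as the reference, with z(0.80) = 0.842.

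**Formulas**, with df = k(n − 1)
- Scheffé critical value: S = √[(k − 1) × F(0.95; k − 1, df)]
- Tukey critical value: T = q(0.95; k, df)/√2
- Relative interval width: S/T. The standard error of a pair is the same under both methods, so it cancels.
- Pairwise familywise error under Scheffé: upper tail of the studentized range (k, df) at S√2
- Power under Scheffé where Tukey has 80%: Φ(T + 0.842 − S), a normal approximation
- Sample size ratio to restore 80%: [(S + 0.842)/(T + 0.842)]²

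**Results at n = 50 per group**

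| k | df | S | T | S/T | Familywise error, pairs | Power under Scheffé | Size ratio |
|---|---|---|---|---|---|---|---|
| 2 | 98 | 1.984 | 1.984 | 1.000 | 0.050 | 80.0% | 1.000 |
| 3 | 147 | 2.473 | 2.368 | 1.044 | 0.038 | 76.9% | 1.067 |
| 4 | 196 | 2.820 | 2.591 | 1.088 | 0.027 | 73.0% | 1.138 |
| 5 | 245 | 3.104 | 2.748 | 1.129 | 0.018 | 68.7% | 1.208 |

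Worked line for k = 4: S/T = 2.820/2.591 = 1.088. Power = Φ(2.591 + 0.842 − 2.820) = Φ(0.613) = 0.730. Size ratio = (3.662/3.433)² = 1.138.

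**Sensitivity to group size.** From n = 20 to n = 100 the familywise error moves only from 0.0387 to 0.0383 (k = 3), 0.0275 to 0.0268 (k = 4) and 0.0186 to 0.0178 (k = 5). The width ratios stay at 1.044, 1.088 and 1.129 to 1.130. The number of groups drives the result; the group size hardly matters.

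**Simulation check.** In 200,000 null data sets for each of k = 3, 4 and 5 at n = 50:
- at least one pair was significant under Scheffé in 0.0383, 0.0268 and 0.0182;
- the overall F test rejected in 0.0498, 0.0499 and 0.0506;
- Tukey alone rejected in 0.0494, 0.0501 and 0.0509;
- Tukey used only after a significant F rejected in 0.045, 0.042 and 0.040;
- no Scheffé pair was significant without a significant F.

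**The case against.** The strongest reply is that Scheffé is a recognised, valid procedure and that choosing it is a preference. It attains 0.05 over all contrasts, tolerates unequal group sizes and never contradicts the overall F test. Section E does not call 0.05 a familywise rate, and Scheffé does not exceed it. Nor does section E restrict the post hoc step to pairs. Section D itself groups precontemplation with contemplation, and preparation with action. Comparing those pooled sets would be a complex contrast, which Scheffé covers and Tukey's pairwise margin does not.

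Much of this stands. Scheffé is not an error here, and it would be wrong to say that it gives nothing in return. The absence of complex contrasts is read from silence, since section E lists no contrasts of any kind. If Tukey is run only after a significant F, its own error also drops below 0.05, so with three groups the gap is 0.038 against 0.045.

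Two parts do not carry. Unequal group sizes give Scheffé no advantage, because Tukey-Kramer also holds 0.05 there. And even gated by the F test, Tukey stays closer to 0.05 than Scheffé at 3, 4 and 5 groups.

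A reader might also infer that the trial's intervention comparison loses power. The document does not support this: effectiveness is tested by ANCOVA and GEE, and Stage 3 has two arms and a success rate as its primary indicator.

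**Conclusion.** The point holds as a minor, conditional loss of efficiency. If three or more groups are compared only in pairs, Scheffé is conservative to the extent tabulated: slight with three groups (about 3 power points) and material with four or five (about 7 and 11 power points). Only at four or more groups could the familywise error fairly be called well below 0.05.

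Squaring the width ratios gives about 9%, 18% and 28% more patients, and a reader might take these as the cost in power. They apply to matching interval width; for power the figures are the 7%, 14% and 21% shown by the size ratios.

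The conclusion rests on an assumed number of groups, on pairs being the only contrasts wanted, and on equal group sizes for the error rates. Use of the ANOVA in Stage 1 is an inference. No conclusion about the interventions depends on it.

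**What to change.** In section E, replace the Scheffé phrase with: Tukey-Kramer pairwise post hoc comparisons. State which variables and stage the ANOVA serves, how many groups it compares, and that 0.05 is the familywise rate for the pairs. Keep Scheffé only for complex contrasts, such as pooled stages of change, and only if these are listed in advance. I would not add a switch to Games-Howell when variances look unequal: without a stated decision rule it turns one prespecified test into a choice made from the data.

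The cost is one phrase and a clarifying sentence, with no extra data. What is given up is coverage of all contrasts and exact agreement with the overall F test: a Tukey pair can be significant when F is not.

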**B. Background**

Smoking is a major risk factor of coronary artery disease (CAD) and is responsible for the death of one in three patients with cardiovascular diseases. Smoking cessation is one of the most favorable methods for reducing the risk of cardiovascular diseases; even for patients with a heart disease, quitting smoking can reduce the chance of a relapse of said disease. However, the Health Promotion Administration revealed that among male patients with acute myocardial infarction (AMI), 79.5% had smoked and 35.6% continued to smoke after an episode of AMI. Although previous studies confirmed that health education and exercises can increase smoking cessation rates, patients' lack of motivation to quit smoking has resulted in a failure rate of 65.5%. Therefore, identifying methods to strengthen patients' motivation to quit smoking is a key to successfully achieving smoking cessation.

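### Does the missing rule for lost smoking outcomes in Stage 3 make the planned GEE analysis wrong?

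*Combined protocol and SAP*

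**What the plan says.** Section D, Stage 3, has patients "randomly divided into experimental or control group" and follows them for "immediate (short-term), three-month, and six month (long-term) health status". It names the main outcome: "The primary indicator used for health status evaluation is smoking cessation success rate".

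Section E is the whole of the analysis plan. It names the software, sets the error level ("The type one error is 0.05"), lists several tests and ends with "ANCOVA and GEE mode will be used to test the effectiveness of intervention respectively". That GEE serves Stage 3 is an inference from the last word of that sentence and from the repeated assessments; the text does not say so directly.

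Nothing in the document states who is in the analysis, what the rate is divided by, how a missing smoking outcome is treated, or which working correlation is used. Nor does it say that only attenders will be analysed.

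**The concern.** A cessation rate needs a denominator, and a patient who has gone back to smoking may well miss a visit. An unweighted GEE drops the missed visit, though not the whole patient. If relapsers miss more visits than abstainers, the estimated rates are too high in both arms. If the link between relapse and absence also differs by arm, the comparison between arms is distorted, and the documents cannot tell us in which direction.

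With no written rule, an analyst could also choose one after seeing the data. The choice can matter: under one assumed loss pattern and no true effect, observed visits and counting missing as smoking give false differences of opposite sign. This is the primary result of the only stage described as randomised, so the question is worth asking.

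**Working it through.** There is no figure in the plan to reproduce: it gives no sample size, power, effect or dropout. The nearest is in section B, where poor motivation is said to have "resulted in a failure rate of 65.5" per cent, and that is background rather than a design input. All success and loss rates below are assumptions.

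**Single-visit calculation.** Let p be true success, L overall loss in an arm, and k the ratio of loss in smokers to loss in abstainers. Loss among abstainers is La = L / (p + (1 - p)k). The rate among those seen is p(1 - La)/(1 - L). The rate with missing counted as smoking is p(1 - La). Take p = 0.30 in both arms, so the true difference is zero, and L = 0.30 (walking) v 0.15 (control).

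- k = 1: La = 0.30 v 0.15. Seen: 0.21/0.70 = 30.0% v 0.255/0.85 = 30.0%, difference 0. Missing as smoking: 21.0% v 25.5%, difference -4.5 points.
- k = 2: La = 0.30/1.7 = 0.1765 v 0.15/1.7 = 0.0882. Seen: 0.2471/0.70 = 35.3% v 0.2735/0.85 = 32.2%, difference +3.1 points, odds ratio 1.15. Missing as smoking: 24.7% v 27.4%, difference -2.6 points.
- k = 2, L = 0.25 in both arms: 0.2559/0.75 = 34.1% in each, odds ratio 1.00.

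In general, the odds ratio among those seen is preserved only if loss depends on the current outcome alone, with the same loss probabilities by outcome in both arms.

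**GEE itself.** The +3.1 points is a single-visit proportion, not a GEE estimate. A three-visit simulation (200,000 per arm, true success 40/35/30% in both arms, latent correlation 0.8, patients not returning once lost) gave, at the last visit:

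- smokers twice as likely to be lost (30.0% v 15.0% overall): independence 33.9% v 31.7% (+2.2 points), exchangeable 31.9% v 30.9% (+1.0);
- only smokers lost, by status at the missed visit (28.6% v 14.7%): 39.6% v 34.4% (+5.2) and 34.5% v 32.3% (+2.2);
- only smokers lost, by previously recorded status (26.4% v 13.6%): 37.2% v 33.1% (+4.1) and 29.4% v 29.8% (-0.4).

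**The rules side by side.** A second run of the same design (400,000 per arm, loss about 30% v 15%) put missing-as-smoking beside both GEE versions. False differences in points:

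| Assumed loss | Independence | Exchangeable | Missing as smoking |
|---|---|---|---|
| Unrelated to smoking | 0 | 0 | about -4.6 |
| Previous status, smokers twice as likely | +1.8 | 0.0 | -3.4 |
| Current status, smokers twice as likely | +2.5 | +1.3 | -3.0 |
| Previous status, only smokers | +4.9 | -0.8 | -1.6 |
| Current status, only smokers | +6.0 | +2.7 | -0.9 |

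Counting missing as smoking has the smallest error only in the last row, the most extreme setting. Exchangeable GEE is as good as or better than both others in the remaining four.

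**The case for a change.** The best case for a change does not depend on size. The primary outcome of a randomised comparison should not be open to a choice of rule once results are known, and a few sentences would settle it. Some loss patterns also favour counting missing as smoking clearly. Take 34.5% true success in both arms (100 - 65.5, from section B), 5% loss of quitters in each arm, and relapser loss of 40% in the walking arm v 20% in control. Those seen then give 0.32775/0.72075 = 45.5% v 0.32775/0.85175 = 38.5%, an odds ratio of 1.33 where the truth is 1.00. Counting missing as smoking gives 32.8% in both arms.

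That arithmetic is right, and so is the observation that the plan is silent. But the result rests on quitters being lost equally in the two arms. Once their loss differs, the same rule produces its own false difference, as the k = 1 and k = 2 cases show. What stands is that a written rule would be tidier. What does not stand is that the planned analysis is wrong, or that the obvious replacement would be more accurate.

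Multiple imputation with less favourable scenarios would add information, but it would supplement the plan rather than correct a rule in it. The size of such scenarios would also need care. Odds of success in missing relative to observed patients (0.45 to 0.24 in these illustrations) cannot be applied directly on top of an imputation model that already uses earlier smoking status.

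**Conclusion.** No change follows. Section E leaves the analysis set, denominator, missing-outcome rule and working correlation unstated, and use of observed visits is how the method ordinarily behaves rather than something the plan prescribes. Analysts can fill this gap sensibly by keeping all randomised patients in their assigned arm, reporting loss by arm and visit, and showing how the result moves under other treatments of missing outcomes.

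Under the assumed 30% v 15% loss and two-fold pattern, the simulated GEE error is about +1.0 to +2.2 points, depending on the working correlation. The closed-form error for counting missing as smoking is -2.6. The observed-visit error vanishes when loss is unrelated to smoking, and it is close to zero with exchangeable correlation when loss follows relapse already recorded. It reaches +5.2 to +6.0 points only with independence correlation and when every lost patient is smoking at the missed visit.

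These figures rest on invented loss and success rates and on the inference that GEE is meant for Stage 3. The documents do not allow the bias in this trial to be sized, or its direction known. The choice between rules is a trade-off that the evidence here does not settle.
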